### **13.4.2. Reporting Adverse Events to the Responsible IEC/IRB and Health Authorities**

Adverse events that meet the IEC/IRB requirements for reporting must be reported within the IEC/IRB's written guidelines. Each clinical site will refer to and follow any guidelines set forth by their Approving IEC/IRB. Each clinical site will refer to and follow any guidelines set forth by their local governing Health Authorities.

The Sponsor will report applicable Adverse Events to the local health authorities according to the written guidelines, including reporting timelines.

### **13.4.3. Event of Special Interest**

None.

### **13.5. Reporting of Pregnancy**

Subjects reporting pregnancy (by self-report) during the study will be discontinued after the event is recorded as an Adverse Event. Once discontinued, pregnant participants and their fetuses will not be monitored for study related purposes. At the Investigator's discretion, the study participant may be followed by the Investigator through delivery. However, this data will not be collected as part of the clinical study database. Pregnant participants are not discontinued from contact lens or solution related studies for safety concerns, but due to general concerns relating to pregnancy and contact lens use. Specifically, pregnant women are discontinued due to fluctuations in refractive error and/or visual acuity that occur secondary to systemic hormonal changes, and not due to unforeseen health risks to the mother or fetus.

## **14. STATISTICAL METHODS**

### **14.1. General Considerations**

Statistical Analysis will be undertaken by the sponsor or under the authority of the sponsor. A general description of the statistical methods to be implemented in this clinical trial is outlined below.

All data summaries and statistical analyses will be performed using the SAS software Version 9.4 (SAS Institute, Cary, NC). Throughout the analysis of data, the results for each subject/eye will be used when available for summarization and statistical analysis. Unscheduled visits will be summarized separately if applicable and will be excluded from the statistical analysis.

Summary tables (descriptive statistics and/or frequency tables) will be provided for all baseline variables, efficacy variables and safety variables as appropriate. Continuous variables will be summarized with descriptive statistics (n, mean, standard deviation (SD), median, minimum and maximum). Frequency count and percentage of subjects or eyes within each category will be provided for categorical data.

This is a feasibility study and further exploratory analysis can be undertaken if necessary at the discretion of the study responsible clinician.

## 14.2. Sample Size Justification

The plan is to enroll 20 subjects with a target of 15 subjects to complete the study. This is a pilot study and the sample size was not based on any empirical power calculation.

The tables below, provided using the POWER procedure in SAS 9.4, summarizes statistical power based on the following assumptions:

- Testing for superiority with 0 VAS points and equivalence with +/- 10 VAS points
- True difference for superiority: 5, 7.5, 10 points and for equivalence: -5, 0, -5 points
- Estimated standard deviations of 15 and 20 points
- Intraclass correlations of 0.4, 0.6, and 0.8
- Two-sided type I error rate of 0.05
- 15 subjects successfully complete the study

Table 3: Power Analysis for the Primary Hypothesis (Superiority)

Difference (Test-Control)	Estimated Standard Deviation	Intraclass Correlation		
		0.4	0.6	0.8
5.0	15	0.300	0.393	0.617
5.0	20	0.211	0.269	0.425
7.5	15	0.515	0.661	0.897
7.5	20	0.351	0.460	0.705
10.0	15	0.724	0.864	0.987
10.0	20	0.515	0.661	0.897

The study is appropriately powered (power above 80%) to show superiority of anesthetized eyes over eyes that received the placebo when the difference in VAS comfort is at least 7.5 points and the intraclass correlation is at least 0.8.

Table 4: Power Analysis for the Primary Hypothesis (Equivalence)

Difference (Test-Control)	Estimated Standard Deviation	Intraclass Correlation		
		0.4	0.6	0.8
-5.0	15	0.259	0.386	0.617
-5.0	20	0.081	0.202	0.422
0.0	15	0.453	0.728	0.974

Difference (Test-Control)	Estimated Standard Deviation	Intraclass Correlation		
		0.4	0.6	0.8
0.0	20	0.117	0.334	0.794
5.0	15	0.259	0.386	0.617
5.0	20	0.081	0.202	0.422

The study is appropriately powered (power above 80%) to show equivalence between comfort scores at post-treatment and 5-minute post-application when there is no difference (0 VAS points) and the intraclass correlation is at least 0.8.

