### 14.5. Primary Analysis

#### VAS Comfort

VAS Comfort score at 5 and 10 minutes post treatment will be analyzed separately using a linear mixed model. The model will include the following experimental design factors: treatment, sequence of treatment, region, sequence of region, period, time event, and first-order carryover as fixed effects. Baseline characteristics such as age and gender may be included as covariates when appropriate. The covariance between residual errors for the same subject across periods will be modeled using one of the following covariance structures: Compound Symmetry (CS) or Unstructured (UN). The covariance structure that returns the lowest Akaike Information Criteria Corrected (AICC) will be selected as the structure that best fits the data. The Kenward and Roger method will be used for the calculation of denominator degrees of freedom.

The null and alternative hypothesis for superiority of anesthetized eyes compared to eyes that received the placebo with respect to VAS comfort at post treatment, where  $\mu_A - \mu_P$  is the difference in VAS comfort between anesthesia and placebo treatments, is as follows:

$$\begin{aligned}H_0: \mu_A - \mu_P &\leq 0 \\H_A: \mu_A - \mu_P &> 0\end{aligned}$$

The hypothesis will be tested via corresponding two-sided 95% confidence interval for least-squares mean difference (anesthesia minus placebo) of VAS comfort. Superiority will be concluded if the lower limit is greater than 0 for at least one of the three ocular regions (upper lid margin, lower lid margin, or cornea).

The null and alternative hypothesis for equivalence of VAS comfort scores at post-treatment and 5-minutes post-application, where  $\mu_1 - \mu_2$  is the difference in VAS comfort score between post-treatment and 5-minutes post-application, is as follows:

$$\begin{aligned}H_0: |\mu_1 - \mu_2| &\geq 10 \\H_A: |\mu_1 - \mu_2| &< 10\end{aligned}$$

The hypothesis will be tested via corresponding two-sided 95% confidence interval for least-squares mean difference (post treatment minus post application) in VAS comfort score. Equivalence will be concluded if the upper limit is less than 10 and the lower limit is greater than  $-10$ .

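### Tables 3 and 4 were computed at one-sided 5% and with a 90% interval, but the plan states two-sided 5% and decides by 95% intervals, so every printed power is too high

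*Combined protocol and SAP*

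**What the plan says.** Section 14.2 (Sample Size Justification) gives the assumptions for Tables 3 and 4: "15 subjects successfully complete the study", "Testing for superiority with 0 VAS points and equivalence with +/- 10 VAS points", SDs of 15 and 20, intraclass correlations of 0.4, 0.6 and 0.8, and "Two-sided type I error rate of 0.05". After Table 3 it claims power above 80% for superiority when the difference in "VAS comfort is at least 7.5 points and the intraclass correlation is at least 0.8". After Table 4 it makes the same claim for equivalence "when there is no difference (0 VAS points) and the intraclass correlation is at least 0.8". Neither sentence mentions the SD.

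Section 14.5 (Primary Analysis, VAS Comfort) sets the decision rules. For superiority: "The hypothesis will be tested via corresponding two-sided 95% confidence interval for least-squares mean difference (anesthesia minus placebo) of VAS comfort", with success if the lower limit is above 0. For equivalence, again from a two-sided 95% interval: "Equivalence will be concluded if the upper limit is less than 10 and the lower limit is greater than" −10. The change-from-pre-treatment analysis in Section 14.5 uses the same 95% interval rule for superiority. Section 14.4 sets an overall type I error rate of 5%. A one-sided 5% test or a 90% interval is not mentioned anywhere.

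**The concern.** A rule that needs the lower limit of a two-sided 95% interval to exceed 0 is a one-sided test at 2.5%. A rule that needs a 95% interval to lie inside ±10 is two one-sided tests at 2.5% each. If the tables used 5% per side, they describe a more lenient test than the one planned, and every value in them overstates the power of the planned comparison.

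The section prints 36 power values and twice calls the study appropriately powered. A null superiority result, or a failure to show equivalence, would be read against those figures. Anyone who sized a later study from them would make it too small.

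**Working it through.** **Inputs, all from Section 14.2.** n = 15 pairs; SD 15 or 20; intraclass correlation (ICC) 0.4, 0.6 or 0.8; superiority against 0; equivalence margin ±10. True differences are 5, 7.5 and 10 for superiority and −5, 0 and 5 for equivalence. (The assumption list prints −5 twice; Table 4 shows −5, 0 and 5.)

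**Formulas.** For one paired comparison:

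- SD of the difference = SD × √(2(1 − ICC)); standard error (SE) = SD of the difference / √15; 14 degrees of freedom.
- Superiority power = P(T > t_crit), with T noncentral t and noncentrality = difference / SE.
- Equivalence power = P(estimate ± t_crit × SE-hat lies inside ±10), integrated over the distribution of the sample variance.
- t_crit = 1.761 at 5% per side and 2.145 at 2.5% per side.

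**Reproducing a Table 3 cell** (difference 7.5, SD 15, ICC 0.8). SD of the difference = 15 × √0.4 = 9.487; SE = 9.487/√15 = 2.449; noncentrality = 7.5/2.449 = 3.062.

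- t_crit 1.761 (one-sided 5%): 0.897, the printed value.
- t_crit 2.145 (95% interval): 0.812.

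**Reproducing a Table 4 cell** (difference 0, SD 20, ICC 0.8). SD of the difference = 20 × √0.4 = 12.649; SE = 12.649/√15 = 3.266.

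- 90% interval (half-width about 1.761 × 3.266 = 5.75): 0.794, the printed value.
- 95% interval (half-width about 2.145 × 3.266 = 7.01): 0.626.

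**All cells.** At 5% per side, all 18 cells of each table match to three decimals (the +5 rows of Table 4 by symmetry). At the stated two-sided 5%, no cell matches; the closest is 0.966 against 0.987 printed. Normal approximations also fail to reproduce Table 3. Trying 13 to 23 pairs on the row for difference 5 and SD 15, only 15 pairs at one-sided 5% reproduces it.

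Table 3, printed → two-sided 0.05:

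| Difference / SD | ICC 0.4 | ICC 0.6 | ICC 0.8 |
|---|---|---|---|
| 5 / 15 | 0.300 → 0.196 | 0.393 → 0.270 | 0.617 → 0.476 |
| 5 / 20 | 0.211 → 0.131 | 0.269 → 0.172 | 0.425 → 0.297 |
| 7.5 / 15 | 0.515 → 0.377 | 0.661 → 0.522 | 0.897 → 0.812 |
| 7.5 / 20 | 0.351 → 0.235 | 0.460 → 0.328 | 0.705 → 0.570 |
| 10 / 15 | 0.724 → 0.592 | 0.864 → 0.766 | 0.987 → 0.966 |
| 10 / 20 | 0.515 → 0.377 | 0.661 → 0.522 | 0.897 → 0.812 |

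Table 4, printed → 95% interval inside ±10:

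| Difference / SD | ICC 0.4 | ICC 0.6 | ICC 0.8 |
|---|---|---|---|
| ±5 / 15 | 0.259 → 0.129 | 0.386 → 0.251 | 0.617 → 0.476 |
| ±5 / 20 | 0.081 → 0.022 | 0.202 → 0.086 | 0.422 → 0.287 |
| 0 / 15 | 0.453 → 0.237 | 0.728 → 0.536 | 0.974 → 0.933 |
| 0 / 20 | 0.117 → 0.032 | 0.334 → 0.146 | 0.794 → 0.626 |

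The largest drop in Table 3 is 0.617 − 0.476 = 0.141 and the smallest is 0.987 − 0.966 = 0.021. In Table 4 they are 0.453 − 0.237 = 0.216 and 0.974 − 0.933 = 0.041.

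**The two summary claims.** At SD 20 and ICC 0.8 the printed tables already give 0.705 (superiority, 7.5 points) and 0.794 (equivalence, 0 points), both below 80%. Under the planned rule these are 0.570 and 0.626.

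**The case against.** **Pilot status.** Section 14.2 says the sample size was not based on a power calculation, so no design choice depends on the tables. That stands and limits the impact. It does not make the printed figures or the two power claims correct.

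**The headline claims survive at SD 15.** They do, at 0.812 and 0.933. Only one cell crosses 80%: superiority at 10 points, SD 15, ICC 0.6, from 0.864 to 0.766. But the claims do not state the SD condition. That omission is a separate wording error, visible in the printed tables whatever the error rate.

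**Success needs only one of three regions.** Section 2.3 words the primary hypotheses that way, and Section 14.5 states no adjustment across regions. If all three regions share the same effect, the chance that at least one passes at the 95% level exceeds the printed single-comparison value. For 7.5 points, SD 15 and ICC 0.8 it is about 0.99 to 0.93 as the correlation between regional differences goes from 0 to 0.7. This limits the finding to one region's comparison, which is what the tables compute. The shared effect and the correlation are assumptions found nowhere in the plan. If only one region responds, the overstatement applies directly.

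**The error may lie in the rule.** Two one-sided tests at 5% each are a recognised convention for equivalence, so the 95% interval may be the slip. That is possible for Table 4, but the table and the rule still disagree. It does not explain Table 3, whose stated error rate is two-sided.

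**Both tails are counted.** The superiority rule looks only at the lower limit. Counting that tail alone changes the recomputed Table 3 cells by at most 0.003 (5 points, SD 20, ICC 0.4: 0.128 rather than 0.131).

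**Conclusion.** The concern holds. Both tables were computed at 5% per side, while the stated assumption and the decision rules imply 2.5% per side. For the single paired comparison that the tables describe, all 36 printed powers are too high. The exact match in every cell identifies the setting used.

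The recomputed figures rest on the plan's own inputs (15 completers and its SDs and correlations). Like the printed tables, they ignore the mixed model and the rule that one region of three is enough. On these figures, superiority power exceeds 80% only at ICC 0.8, with 7.5 points and SD 15 or with 10 points at either SD. Equivalence power exceeds 80% only at zero difference, SD 15 and ICC 0.8.

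**What to change.** Make one of two changes before data are seen.

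1. **Keep the 95% rules.** Replace Tables 3 and 4 with the recomputed values above. If Table 3 is to reflect strictly a lower limit above 0, five cells fall slightly: 5/15 at ICC 0.4 and 0.6 to 0.195 and 0.269, 5/20 at ICC 0.4 and 0.6 to 0.128 and 0.171, and 7.5/20 at ICC 0.6 to 0.327. Restate the two power claims with the conditions given in the verdict.
2. **Keep the tables.** State the error rate as one-sided 5% in Section 14.2, and change the intervals in Section 14.5 to 90%, with the overall error rate in Section 14.4 made consistent. The SD condition must still be added: superiority at 7.5 points and equivalence at 0 points, both at ICC 0.8, exceed 80% only at SD 15.

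In either case, say that the tables refer to one region's comparison, and correct the repeated −5 in the assumption list. The cost is protocol text and two tables, with no extra subjects or procedures. Under the first option the stated power becomes less favourable; under the second, the decision rules become more lenient.

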## 2.3. Hypotheses

### Primary Hypotheses

1. Post-treatment subjective scores of comfort (VAS scale) for anesthetized eyes are superior to eyes that received the placebo for at least one of the ocular regions (upper lid margin, lower lid margin, or cornea).
2. Comfort change from pre-treatment for anesthetized eyes is superior to eyes that received the placebo for at least one of the ocular regions (upper lid margin, lower lid margin, or cornea).
3. Post-treatment subjective scores of comfort (VAS scale) for anesthetized eyes are equivalent to 5-minute post lens application levels in the morning for at least one of the ocular regions (upper lid margin, lower lid margin, or cornea). An equivalence margin of 10 points will be used.

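### Tables 3 and 4 give single-region power at 0.05 per side, whereas the primary hypotheses can succeed in any of three regions judged by 95% intervals, and hypothesis 3 has two differing success rules

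*Combined protocol and SAP*

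**What the plan says.** The two tables in section 14.2 are titled "Table 3: Power Analysis for the Primary Hypothesis (Superiority" and "Table 4: Power Analysis for the Primary Hypothesis (Equivalence" (closing brackets omitted here). Neither title names a region. The listed assumptions include "15 subjects successfully complete the study", "Two-sided type I error rate of 0.05" and "Testing for superiority with 0 VAS points and equivalence with +/- 10 VAS points", with SDs of 15 and 20 and intraclass correlations of 0.4, 0.6 and 0.8. Under each table a sentence claims more than 80% power. For superiority the claim applies from 7.5 points upward with a correlation of at least 0.8. For equivalence it applies at a true difference of zero with the same correlation. Neither sentence names the SD.

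Section 2.3 makes all three primary hypotheses any-region hypotheses. Item 3 asks that post-treatment scores be "equivalent to 5-minute post lens application levels in the morning for at least one of the ocular regions".

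Section 14.5 (VAS Comfort) decides by two-sided 95% confidence intervals. For superiority the region clause is there: "Superiority will be concluded if the lower limit is greater than 0 for at least one of the three ocular regions". For equivalence the rule gives only the limits, "Equivalence will be concluded if the upper limit is less than 10 and the lower limit is greater than" −10, and mentions no region.

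**The concern.** The two sentences on power are the plan's only statement of what 15 completers can show. A reader takes a table labelled for the primary hypothesis to give the chance of meeting that hypothesis as written. The tables differ from the written rule in two ways: they cover one comparison where the rule allows three, and they are computed at a looser level than the intervals in section 14.5. These act in opposite directions, so the printed figure may be too high or too low, depending on how many regions respond and how strongly visits correlate.

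Separately, hypothesis 3 has one success rule in section 2.3 (any region) and another in section 14.5 (a single unqualified interval). With three regions in the data, an analyst could apply the section 14.5 rule to a pooled contrast or region by region and reach a different answer from section 2.3.

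**Working it through.** **Inputs.** All are from section 14.2: n = 15 pairs (14 df), SD 15 or 20, ICC 0.4, 0.6 or 0.8, superiority bound 0, equivalence margin ±10. The between-visit correlation of the paired differences is not in the plan. It is an assumption here, varied from 0 to 0.9.

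**Step 1: reproduce the plan's figures.** SD of a paired difference = SD × √(2(1 − ICC)). For SD 20 and ICC 0.8 this is 20 × √0.4 = 12.65, and the standard error is 12.65/√15 = 3.266.

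- Superiority, 7.5 points: noncentrality 7.5/3.266 = 2.296. With the one-sided 0.05 critical value (1.761), noncentral-t power is 0.705, as printed.
- Equivalence, true difference 0: two one-sided tests at 0.05 each (a 90% interval), integrated over the sample variance, give 0.794, as printed.

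The same calculation matches all 36 cells of the two tables to three decimals. The tables are therefore power for one contrast at 0.05 per side. They do not match at the two-sided 0.05 stated in section 14.2.

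**Step 2: one region at the section 14.5 level.** A two-sided 95% interval puts 0.025 on each side (critical value 2.145).

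| Case (ICC 0.8) | Printed | One region, 95% interval |
|---|---|---|
| Superiority 7.5, SD 15 | 0.897 | 0.812 |
| Superiority 7.5, SD 20 | 0.705 | 0.570 |
| Equivalence 0, SD 15 | 0.974 | 0.933 |
| Equivalence 0, SD 20 | 0.794 | 0.626 |

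**Step 3: any of three regions, 95% interval, SD 20, ICC 0.8.** Unrounded one-region power for superiority is 0.5705.

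- Superiority, all three respond, independent visits: 1 − 0.4295³ = 0.921. By simulation with correlated visits: about 0.87 at correlation 0.3, 0.80 at 0.6 and 0.68 at 0.9.
- Superiority, one responds, independent visits: 1 − 0.4295 × 0.975² = 0.592. Positive correlation pulls this back toward 0.570.
- Equivalence, true difference 0 in all three, independent visits: 1 − (1 − 0.626)³ = 0.948. By simulation: about 0.82 at correlation 0.8 and 0.77 at 0.9.

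**Step 4: separate the two causes.** Hold alpha at the tables' own 0.05 per side. With one responder and independent visits, any-of-three power is 1 − 0.295 × 0.95² = 0.734, above the printed 0.705. Hold alpha at 0.025 per side and the region rule moves 0.570 up to 0.592. The region rule raises power at either level. The fall from 0.705 to 0.592 is due to the change of alpha.

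**Step 5: the two claims of more than 80% power.** Even as printed, both fail at SD 20 (0.705 and 0.794) and hold only at SD 15. At the 95% interval, the per-region figures at SD 15 still pass (0.812 and 0.933), and those at SD 20 fall to 0.570 and 0.626.

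**The case against.** Per-comparison power is a common way to report, and section 14.2 says that the sample size of this pilot was not based on a power calculation. At a fixed alpha, any-of-three power cannot be below one-region power, so a per-region table is a conservative floor. This stands. A reader might infer that the any-region rule itself makes the printed figures too high; step 4 shows that it does not.

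The missing equivalence clause may be a simple omission, since section 2.3 already fixes the rule. That is plausible, and it is why the repair is one phrase. A reader might go further and take section 14.5 to require equivalence in all three regions, with far lower power. No section says so, and that reading should not be used. Nor is the missing clause what separates Table 4 from section 14.5. An unqualified interval can be read as one contrast, which is Table 4's structure; on that reading the mismatch is the 90% against the 95% interval.

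The any-of-three figures also have limits. They need a correlation that the plan does not give. At high correlation some printed cells come close to any-of-three power by coincidence: for 7.5 points, SD 15 and ICC 0.8, 0.897 is printed against about 0.91 at correlation 0.8. They also apply to one time point, whereas section 14.5 analyses 5 and 10 minutes separately and gives no rule for combining them.

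**Conclusion.** The point holds in a limited form. The tables are labelled for hypotheses whose success rules they do not describe, and hypothesis 3 is written with two rules that must be reconciled. Against the written 95% rule at 7.5 points, SD 20 and ICC 0.8, the printed 0.705 is too high if one region responds (0.592 at most for non-negative correlation). If all three respond it is too low over most of the assumed correlation range (0.92 at 0, about 0.80 at 0.6) and slightly too high at 0.9 (about 0.68). For equivalence at zero difference, SD 20 and ICC 0.8, the printed 0.794 compares with 0.626 for one region and 0.948 for any of three if visits are independent.

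These figures assume 15 completers, the plan's SDs and ICCs, and a paired t approximation to the planned mixed model. The any-of-three figures also assume equal effects in the responding regions. The practical consequence is modest, because enrolment was not derived from the tables. What must change is the statement of what the study can show and the rule for hypothesis 3.

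**What to change.** 1. In the equivalence rule of section 14.5, add the same at-least-one-region clause that the superiority rule carries, so that it matches item 3 of section 2.3.
2. Relabel Tables 3 and 4 as power for a single region, and recompute them at the 95% interval that section 14.5 uses, or at an adjusted level if one is adopted for the three regions.
3. Add any-of-three power at that level over a stated range of between-visit correlation, for superiority with an effect in all three regions and with an effect in one only, and for equivalence under stated true differences.
4. Rewrite the two sentences claiming more than 80% power from those figures, and name the SD to which each applies.

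The cost is a wording change and a short recalculation. There are no extra subjects or procedures, and the sample size stays as it is. The downside is that the per-region figures become less favourable, for example 0.897 to 0.812 and 0.794 to 0.626.
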